**CONFIDENTIAL**

056-F275 Rev E Clinical Investigation Plan Template

# Reveal LINQ™ for COPD Study Clinical Investigation Plan

Version 5.0,  
1-DEC-22

Page 55 of 79

Medtronic

	In order to establish the non-relatedness, not all the criteria listed above might be met at the same time, depending on the type of device/procedures and the event.
Unlikely	The relationship with the use of the device seems not relevant and/or the event can be reasonably explained by another cause, but additional information may be obtained.
Possible	The relationship with the use of the investigational device is weak but cannot be ruled out completely. Alternative causes are also possible (e.g. an underlying or concurrent illness/ clinical condition or/and an effect of another device, drug or treatment). Cases where relatedness cannot be assessed or no information has been obtained should also be classified as possible.
Probable	The relationship with the use of the investigational device seems relevant and/or the event cannot reasonably be explained by another cause, but additional information may be obtained.
Causal Relationship	
The event is associated with the device or study procedures beyond reasonable doubt when:
 

• The event is a known side effect of the product category the device belongs to or of similar devices and procedures;

• The event has a temporal relationship with device use/application or procedures;

• The event involves a body-site or organ that the device or procedures are applied to or the device or procedures have an effect on;

• The serious event follows a known response pattern to the medical device (if the response pattern is previously known);

• The discontinuation of medical device application (or reduction of the level of activation/exposure) and reintroduction of its use (or increase of the level of activation/exposure) impact on the serious event (when clinically feasible);

• Other possible causes (e.g., an underlying or concurrent illness/clinical condition or/and an effect of another device, drug, or treatment) have been adequately ruled out;

• Harm to the subject is due to error in use;

**Medtronic Business Restricted**

**CONFIDENTIAL**

056-F275 Rev E Clinical Investigation Plan Template

# Reveal LINQ™ for COPD Study Clinical Investigation Plan

Version 5.0,  
1-DEC-22

Page 56 of 79

Medtronic

	

• The event depends on a false result given by the device used for diagnosis (when applicable);

 
In order to establish the relatedness, not all the criteria listed above might be met at the same time, depending on the type of device/procedures and the serious event.

Seriousness	
Serious Adverse Event (SAE) (ISO 14155:2020 section 3.45)	
An AE that:
 

• Led to death

• Led to a serious deterioration in the health of the subject, resulting in:

◦ A life-threatening illness or injury, or

◦ A permanent impairment of a body structure or a body function, or

◦ In-patient or prolonged hospitalization, or

◦ Medical or surgical intervention to prevent life-threatening illness or injury or permanent impairment to a body structure or a body function,

• Led to fetal distress, fetal death or a congenital abnormality or birth defect.

 
Note: Planned hospitalization for a pre-existing condition, or a procedure required by the CIP, without serious deterioration in health, is not considered a SAE.

Serious Adverse Device Effect (SADE) (ISO 14155:2020 section 3.44)	Adverse device effect that has resulted in any of the consequences characteristic of a serious adverse event.
Complication	
An adverse event that includes the following is considered a complication:
 

• Results in death,

• Involves any termination of significant device function, or

• Requires an invasive intervention

 
Non-invasive (21 CFR 812): when applied to a diagnostic device or procedure, means one that does not by design or intention:
 

• Penetrate or pierce the skin or mucous membranes of the body, the ocular cavity, or the urethra, or

**Medtronic Business Restricted**

**CONFIDENTIAL**

056-F275 Rev E Clinical Investigation Plan Template

# Reveal LINQ™ for COPD Study Clinical Investigation Plan

Version 5.0,  
1-DEC-22

Page 57 of 79

Medtronic

	
 
○ Penetrate: to pass, extend, pierce, or diffuse into or through something; to enter by overcoming resistance; to gain entrance to
 
○ Pierce: to force a way into or through something
 
● Enter the ear beyond the external auditory canal, the nose beyond the nares, the mouth beyond the pharynx, the anal canal beyond the rectum, or the vagina beyond the cervical os
 
 
Note (FDA): Blood sampling that involves simple venipuncture is considered noninvasive, and the use of surplus samples of body fluids or tissues that are left over from samples taken for non- investigational purposes is also considered noninvasive.
						
Observation	
Any Adverse Event that is not a complication.
 
Note 1: Pulmonary related AEs will be the only AEs requiring classification of either Complication or Observation by Sponsor and EAC.
						
Unanticipated Adverse Device Effect (UADE) (21 CFR 812.3(s))	
Any serious adverse effect on health or safety or any life-threatening problem or death caused by, or associated with, a device, if that effect, problem, or death, was not previously identified in a nature, severity, or degree of incidence in the investigational plan or application (including a supplementary plan or application), or any other unanticipated serious problem associated with a device that relates to the rights, safety, or welfare of subjects.
						
Other							
Unavoidable Adverse Event	
An Adverse Event inherent to a surgical procedure that is expected to occur in all subjects for a projected duration according to the Investigator's opinion, including, but not limited to:
 
  
 Event Description	Timeframe (hours) from the Surgical Procedure	
   
 Pocket site / Incisional pain	72	
 
 Mild to moderate bruising / ecchymosis	168	
  
	Event Description	Timeframe (hours) from the Surgical Procedure	Pocket site / Incisional pain	72	Mild to moderate bruising / ecchymosis	168
Event Description	Timeframe (hours) from the Surgical Procedure						
Pocket site / Incisional pain	72						
Mild to moderate bruising / ecchymosis	168						

**Medtronic Business Restricted**

**CONFIDENTIAL**

056-F275 Rev E Clinical Investigation Plan Template

## 12.5 Reporting of Adverse Events

To ensure that all AEs that are potentially relevant are collected, the following subset of AEs will be collected throughout a subject's participation, starting at the time the informed consent form is signed:

- All Reveal LINQ™ Procedure related AEs
- All Reveal LINQ™ System related AEs
- All Serious AEs
- All Pulmonary related AEs
- All Cardiovascular related AEs

Reporting of AEs to Medtronic will occur on an Adverse Event e-CRF, including a description of the event, the diagnosis, the date of event onset, the date the site became aware of the event, the relatedness and seriousness of the event, diagnostic tests and procedures performed, actions taken as a result of the event, and outcome of the event. Each AE must be recorded on a separate AE eCRF. Subject deaths are also required to be reported and should be collected on an AE CRF with a Fatal outcome. Refer to section 12.6 for subject death collection and reporting requirements.

Documented pre-existing conditions are not considered AEs unless the nature or severity of the condition has worsened post implant. In all geographies, unavoidable adverse events, listed in Table 10, need not be reported unless the adverse event worsens or is present outside the stated timeframe.

### 12.5.1 Adverse Event and Device Deficiency Classification

All reported AEs and DDs will be reviewed by a Medtronic representative. Adverse events will be classified according to the standard definitions as outlined in Table 9.

Upon receipt of AEs and DDs at Medtronic, a Medtronic representative will review the AE/DD for completeness and accuracy and when necessary will request clarification and/or additional information from the investigator. Medtronic will utilize the Medical Dictionary for Regulatory Activities (MedDRA), to assign a MedDRA term for each AE based on the information provided by the investigator.

Regulatory reporting of AEs and DDs that could have led to a SADE will be completed according to local regulatory requirements. Refer to Table 11 for a list of required investigator and Medtronic reporting requirements and timeframes. It is the responsibility of the investigator to abide by any additional AE reporting requirements stipulated by the IRB/EC responsible for oversight of the study at their site.

For emergency contact regarding a SAE and/or SADE, contact a Medtronic study representative immediately (refer to the study contact list provided in the site's study documents binder/investigator site file or refer to the Sponsor Contact Information section provided in the CIP).

An Event Adjudication Committee (EAC) will review the Pulmonary related AEs and will provide a COPD event relatedness adjudication and a Complication or Observation classification for each Pulmonary

related event. The EAC will additionally be providing a death classification for all reported AEs with an outcome of fatal.

**Table 10: Adverse Event Classification Responsibilities**

What is classified?	Who classifies?	Classification Parameters
Relatedness	Investigator	Reveal LINQ™ system related, Reveal LINQ™ procedure related, Pulmonary Related, Cardiovascular related
	Sponsor	Reveal LINQ™ system related, Reveal LINQ™ procedure related, Pulmonary Related, Cardiovascular related, Heart Failure Event, COPD event
Seriousness	Investigator	SAE, Device Deficiency with SADE potential
	Sponsor	SAE, Device Deficiency with SADE potential, UADE, Complication/Observation
AE Term (Diagnosis)	Investigator	Based on presenting signs and symptoms and other supporting data
	Sponsor	MedDRA term assigned based on the term provided by Investigator
Death Classification	Investigator	Sudden Cardiac, Non-sudden Cardiac, Non-Cardiac, Unknown

## 12.5.2 Adverse Event and Device Deficiency Reporting Requirements

Regulatory reporting of AEs and DDs will be completed according to local regulatory requirements. Investigator and sponsor reporting requirements are outlined in Table 11. It is the responsibility of the investigator to abide by the adverse event and device deficiency reporting requirements stipulated by local law and the site's IRB/EC.

For adverse events and device deficiencies that require immediate reporting, initial reporting may be completed by contacting the study sponsor (refer to the study contact list provided in the site's study documents binder/investigator site file or refer to the contact information provided in Table 1).

**Table 11: Reporting Requirements**

Serious Adverse Device Effects (SADEs)	
Investigator submit to:	
Medtronic	Submit as soon as possible as per local reporting requirement, but not later than within 10 working days after the investigator first learns of the event.
IRB/Ethics Committee	Submit per local reporting requirement.
Regulatory Authorities	Submit per local reporting requirement.

**Medtronic Business Restricted**

# Reveal LINQ™ for COPD Study Clinical Investigation Plan

Version 5.0,  
1-DEC-22

Page 60 of 79

Medtronic

Sponsor submit to:	
Regulatory Authorities	Submit as soon as possible as per local reporting requirement, but not later than within 10 working days after the investigator first learns of the event.
IRB/Ethics Committee	Submit per local reporting requirement.
Serious Adverse Events (SAE)/ Adverse Device Effects (ADE)	
Investigator submit to:	
Medtronic	Submit as soon as possible as per local reporting requirement, but not later than within 10 working days after the investigator first learns of the event.
Regulatory Authorities	Submit per local reporting requirement.
IRB/Ethics Committee	Submit per local reporting requirement.
Sponsor submit to:	
Regulatory Authorities	Submit per local reporting requirement.
IRB/Ethics Committee	Submit per local reporting requirement.
All other AEs	
Investigator submit to:	
Medtronic	Submit as soon as possible as per local reporting requirement after the investigator first learns of the event.
Regulatory Authorities	Submit per local reporting requirement.
IRB/Ethics Committee	Submit per local reporting requirement.
Sponsor submit to:	
Regulatory Authorities	Submit per local reporting requirement.
IRB/Ethics Committee	Submit per local reporting requirement.
Device Deficiency with SADE potential	
Investigator submit to:	
Medtronic	Submit as soon as possible as per local reporting requirement, but not later than within 48 hours after the investigator first learns of the event.
Regulatory Authorities	Submit per local reporting requirement.
IRB/Ethics Committee	Submit per local reporting requirement.
Sponsor submit to:	
Regulatory Authorities	Submit per local reporting requirement.
IRB/Ethics Committee	Submit per local reporting requirement.
All other Device Deficiencies	
Investigator submit to:	
Medtronic	Submit as soon as possible as per local reporting requirement, but not later than within 48 hours after the investigator first learns of the event.
Regulatory Authorities	Submit per local reporting requirement.
IRB/Ethics Committee	Submit per local reporting requirement.

*Medtronic Business Restricted*

**CONFIDENTIAL**

056-F275 Rev E Clinical Investigation Plan Template

## 12.6 Subject Death

All subject deaths must be reported by the investigator to Medtronic on an AE form (AE with fatal outcome) as soon as possible after the investigator first learns of the death. In case of death, there should be one AE CRF with an outcome of fatal.

In the event of a subject's death, the inserted system should be explanted and returned to Medtronic for analysis whenever possible. Local laws and procedures must be followed where applicable. If any device or system component is returned to Medtronic, internal returned product reporting systems may be used to gather additional information about the returned device/component.

A copy of the death certificate, if available and allowed by state/local law, should be sent to the Medtronic clinical study team. When a death occurs in a hospital, a copy of the death summary report and all relevant hospital records should be sent to the Medtronic clinical study team, if available. If an autopsy is conducted, the autopsy report should also be sent to the Medtronic clinical study team if available and allowed by state/local law. When the death occurs at a remote site, it is the investigative site's responsibility to attempt retrieval of information about the death. Additionally, device disposition information should be updated. In summary, the following data will be collected:

- Date of death
- Detailed description of death
- Cause of death
- Relatedness to system and/or procedure
- Device interrogation (if available, postmortem preferred)
- Death summary/hospital records (if available and allowed by state/local law)
- Autopsy report (if available and allowed by state/local law)
- Death certificate (if available and/or allowed by state/local law)

### 12.6.1 Death Classification and Reporting

Sufficient information will be required in order to properly classify the subject's death.

The Investigator shall classify each subject death per the following definitions:

Cardiac Death: A death directly related to the electrical or mechanical dysfunction of the heart.

Sudden Cardiac Death (SCD): Natural death due to cardiac causes, indicated by abrupt loss of consciousness within one hour of the onset of acute symptoms; preexisting heart disease may have been known to be present, but the time and mode of death are unexpected. If time of onset cannot be determined, SCD will alternatively be defined as any unexpected cardiac death occurring out of the hospital or in the emergency room as dead on arrival.

Non-sudden Cardiac Death: All cardiac deaths that are not classified as sudden deaths, including all cardiac deaths of hospitalized subjects on inotropic support.

Non-cardiac Death: A death not classified as a cardiac death.

Unknown Cardiac Classification: Unknown death classification is intended for use only when there is insufficient or inadequate information to classify the death.

The EAC will review all AEs with a fatal outcome and provide a final adjudication of both COPD event and death classification. Regulatory reporting of subject deaths will be completed according to local regulatory requirements. Refer to Table 11 for investigator and sponsor reporting requirements and timeframes.

## 12.7 Product Complaint Reporting

In geographies where devices are market-released, product complaint reporting is applicable. This includes when an AE is related to a market-released device during the study. The reporting of product complaints is not part of the clinical study and should be done in addition to the Adverse Event reporting requirements. Refer to local regulations for reporting requirements.

**Product Complaint:** Any written, electronic or oral communication that alleges deficiencies related to the identity, quality, durability, reliability, safety, effectiveness or performance of a medical device that has been placed on the market.

It is the responsibility of the investigator to report all product complaint(s) associated with a medical device distributed by Medtronic, regardless whether they are related to intended use, misuse or abuse of the product. Reporting must be done immediately and via the regular channels for market-released products.

Medtronic will notify the regulatory authorities, as applicable for the following incidents immediately upon learning of them:

- Any malfunction or deterioration in the characteristics and/or performance of a device, as well as any inadequacy in the labeling or instructions for use which led or might have led to the death or serious deterioration in the state of health of a patient, user, or other person.
- Any technical or medical reason resulting in withdrawal of a device from the market by the manufacturer.

## 13. Data Review Committees

### 13.1 Event Adjudication Committee

At regular intervals, an Event Adjudication Committee (EAC) will review and adjudicate at a minimum, all events classified by the investigator or Medtronic as Pulmonary related and all AEs with a fatal outcome. The EAC will provide an adjudication for COPD event and a Complication or Observation classification for all AEs that are reviewed. The EAC will additionally provide a death classification for all AEs with an outcome of fatal. The EAC will consist of a non-Medtronic employed physicians that are not participating investigators for the study.

Medtronic personnel may facilitate and participate in an EAC meeting but will be non-voting members.

For all adverse events reviewed by the EAC, Medtronic will provide the EAC with the investigator's description and classification. The EAC is responsible for reviewing the investigator's assessment and supportive documentation (when available), reviewing applicable definitions, and determining final classifications for all adjudication parameters.

## 13.2 CRO

CRO and core lab information is provided below. This information is subject to change during the clinical study. Periodic updates to CRO and core labs information will be sent to the centers as needed.

## 14. Statistical Design and Methods

The LINQ™ for COPD is a prospective, non-randomized, multi-center, observational, pre-market clinical study. The purpose of the study is to characterize the Reveal LINQ™ derived data from patients with COPD.

This is a feasibility study that is exploratory in nature and with no hypothesis. Therefore, justification on sample size is not required. The study plans to enroll up to 100 subjects from up to 10 centers in the United States, with no more than 20 subjects enrolled per site. Enrolled subjects are expected to be followed up for at least 12 months after the insertion of Reveal LINQ™ device and download of either the LINQ HF or ALLEViate-HF investigational RAMware. The expected total study duration is approximately 33 months, representing approximately 26 months of patient enrollment and 6 months of subject follow-up with up to 1 month between enrollment and insertion.

### 14.1 General Aspects of Analysis

Medtronic statisticians or designees will perform all statistical analyses.

The study is exploratory in nature with no formal statistical hypothesis planned. A separate Statistical Analysis Plan (SAP) will be developed and include a comprehensive description of the statistical methods and analyses to be included in the final study report. Any change to the data analysis methods described in the protocol will require an amendment only if it changes a principal feature of the protocol. Any other change to the data analysis methods described in the protocol, and the justification for making the change, will be described in the clinical study report.

*Medtronic Business Restricted*

## 14.2 Analysis Execution

The study objective will be analyzed after the last subject exits the study.

## 14.3 Primary Objective

The primary objective is to characterize Reveal LINQ™ derived data from patients with COPD by assessing the relationship between changes in LINQ™ derived data with subsequent COPD events.

### 14.3.1 Hypothesis

There is no statistical hypothesis for this objective.

### 14.3.2 Endpoint Definition

The COPD events as adjudicated by the EAC will be used in the analysis. In the case where a subject has multiple COPD events per EAC adjudication during the study, all the COPD events of the subject will be included in the analysis.

According to section 5.1, COPD event is defined as an adverse event where the underlying COPD condition exacerbates beyond normal day-to-day variations, where an increase in dyspnea, cough, and/or sputum production presents with acute onset and necessitates supplementing regular COPD medications with antibiotics for respiratory pathogens and/or steroids.

### 14.3.3 Analysis Methods

Data from multiple study components will be collected in this study, of which the Reveal LINQ™ HF derived data is of the most interest. This includes subcutaneous electrocardiogram, impedance, temperature, accelerometer and patient activity measurements.

Descriptive statistics such as mean and standard deviation for continuous variables and count and proportion for categorical variables will be used to summarize the derived data from Reveal LINQ™ HF. The relationship between changes in LINQ™ derived data and COPD events per EAC adjudication will be evaluated. Specifically, for each subject that has experienced at least one COPD event per EAC adjudication, the average daily measurements of LINQ™ derived data before and after a COPD event will be plotted to identify patterns and signals related to the occurrence of the COPD event.

Baseline data such as demographics, medical history, physical exam (heart rate, blood pressure, weight, spirometry assessment, etc.), and blood measurements (Creatinine, BNP, NT-pro BNP, White Blood Cells and Eosinophils) will also be summarized using descriptive statistics.

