**Medtronic Business Restricted**

**CONFIDENTIAL**

056-F275 Rev E Clinical Investigation Plan Template

	
Scheduled In-office Follow-up Visit (optional): Baseline Measurements, medication assessment, device interrogation (save to media via USB) (pre and post visit procedures), spirometry tests with Holter, patient assistant activity, Chest x-ray, adverse events, device deficiencies, study deviations
 
Study Exit Visit: Reason for exit, removal of LINQ HF or ALLEViate-HF RAMware from LINQ™ device, device interrogation (save to media via USB), opting out of the subject diary, SGRQ, Medication assessment, labs, adverse events, device deficiencies, study deviations
 
Additionally, up to 20 subjects will be asked to place an EMFIT monitor under their bed for the length of their study participation, with no more than 10 subjects per site. Furthermore, LINQ™ device data will be collected bi-weekly via CareLink manual transmissions as well as system modifications and subject deaths will be collected.

Safety Assessments	All LINQ™ system and procedure-related adverse events (AEs), all serious adverse events (SAEs), all Pulmonary related AEs and all Cardiovascular related AEs will be collected throughout the study duration of a subject's participation in the study, beginning at the time of informed consent. An Event Adjudication Committee (EAC) will conduct a medical review of all adverse events classified by the investigator or Medtronic as Pulmonary related and all AEs with a fatal outcome. The EAC will consist of non-Medtronic employed physicians that are not participating investigators for the study.
Statistics	Since the study will be exploratory in nature and the study objectives are descriptive, no clinical endpoints will be developed. LINQ™ derived data will be summarized using descriptive statistics. Their relationship to COPD events (per EAC adjudication) will be evaluated by looking at the data before and after the occurrence of COPD events to identify potential patterns and signals.

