## 14.4 Sample Size Determination

There are no sample size requirements as this is an observational study with no hypothesis for the study objective. A sample size of up to 100 enrolled subjects was selected assuming sufficient data can be collected from this cohort to explore the relationship between changes in LINQ™ derived data with COPD events.

According to a review by Seemungal et al., the annual rates of COPD exacerbations were estimated to be as low as 0.5 to a high of 3.5 exacerbations per patient from several studies, and hospitalization rates ranged from as low as 0.09 to 2.4 per patient per year. This study requires that a subject should have 2 COPD exacerbations within the previous 12 months as one of the inclusion criteria. Assuming the COPD exacerbation rate remains as 2 COPD exacerbations per patient year after subjects are enrolled, a group of 60 enrolled subjects being followed up for 12 months after successful insertion of Reveal LINQ™ device and download of the investigational RAMware would expect to have 120 COPD exacerbations. Assuming 50% of the COPD exacerbations would meet the study definition of “COPD event”, a total of 60 COPD events would be expected.

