7.9.3 Analysis Methods

Data from multiple study components will be collected in this study, of which the Reveal LINQ™ HF derived data is of the most interest. This includes subcutaneous electrocardiogram, impedance, temperature, accelerometer and patient activity measurements.

Descriptive statistics such as mean and standard deviation for continuous variables and count and proportion for categorical variables will be used to summarize the derived data from Reveal LINQ™ HF. The relationship between changes in LINQ™ derived data and COPD events per EAC adjudication will be evaluated. Specifically, for each subject that has experienced at least one COPD event per EAC adjudication, the average daily measurements of LINQ™ derived data before and after a COPD event will be plotted to identify patterns and signals related to the occurrence of the COPD event.

In addition, exploratory survival analyses for time to first COPD event through 12-months of follow-up such as a Kaplan-Meier curve and Cox proportional hazards regression models with independent variables such as demographics and comorbidities will be included.

Each subject's time to first detected and adjudicated COPD event will be defined as the time from insertion date to the onset date of first COPD event. Subjects who have not experienced a COPD event through 12 months will be censored at:

- (1) their point of last contact, usable Reveal LINQ ICM interrogation or CareLink transmission if they occur before or at 12 months, whichever is later

or

- (2) 12 months (374 days) if their point of last contact, usable Reveal LINQ ICM interrogation or CareLink transmission go beyond 12 months.

Survival estimates and hazard rate with 95% confidence intervals will be reported.

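### Device data are related to COPD events only through before-and-after plots in subjects with an event; no event-free time is designated as a reference, so the analysis cannot show whether a pre-event pattern is more common than in stable time

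*Protocol*

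**What the plan says.** The primary objective (protocol 5.1.1 and 14.3, SAP 4.1) is the relationship between changes in LINQ data and subsequent COPD events. Protocol 4.2 adds that the data are meant to support a prediction algorithm.

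Three places describe how the relationship is assessed, and all describe the same thing:

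- Protocol 14.3.3: "for each subject that has experienced at least one COPD event per EAC adjudication, the average daily measurements of LINQ™ derived data" are plotted before and after an event.
- SAP 7.9.3: values "before and after a COPD event will be plotted to identify patterns and signals related to the occurrence of the COPD event".
- Protocol synopsis, Statistics: the relationship is "evaluated by looking at the data before and after the occurrence of COPD events to identify potential patterns and signals".

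Protocol 14.3.2 requires that "all the COPD events of the subject will be included in the analysis". Protocol 14.6 and SAP 7.4 require device data on both sides of onset but give no window length, baseline or reference period.

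Two other analyses are planned. The device data are summarised overall, with no split by event status or period. SAP 7.9.3 also adds time-to-first-event analyses, in which "Cox proportional hazards regression models with independent variables such as demographics and comorbidities will be included"; no device variable is named.

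**The concern.** A change in a sensor signal is related to later events only if it is found more often, or is larger, before events than at other times. Plots built around events show what happened before events. They do not show how often the same thing happens when no event follows. A pattern equally common in stable time could therefore be carried forward as a signal, and false alarms in stable time are what a prediction algorithm most needs to control.

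The days after an event are not a neutral substitute. By the definition in protocol 14.3.2, the event "necessitates supplementing regular COPD medications with antibiotics for respiratory pathogens and/or steroids", so those days reflect both recovery and added treatment.

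Subjects without an event are in the analysis set (protocol 14.3.4), but the plots leave them out.

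**Working it through.** **1. The plan's own figure.** Protocol 14.4 takes 60 subjects, 12 months and 2 exacerbations per patient-year: 60 × 2 × 1 = 120. "Assuming 50% of the COPD exacerbations would meet the study definition", so 120 × 0.5 = 60 COPD events. Both figures reproduce. The implied rate is 60 / 60 = 1 COPD event per patient-year.

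**2. Subjects who never enter the plots.**

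- Poisson, 12 months: exp(−1) = 0.368; 60 × 0.368 = 22 subjects.
- Gamma-mixed Poisson (assumed overdispersion), 12 months: shape 2 gives 1.5^−2 = 0.444; shape 0.5 gives 3^−0.5 = 0.577.
- Poisson, follow-up assumed uniform from 6 to 32 months (26 months of enrollment, at least 6 of follow-up, protocol 6.1): (exp(−0.5) − exp(−2.667)) / 2.167 = 0.248.

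**3. What the plots leave open.** Suppose a pattern precedes 42 of 60 events (70%, assumed). In 30-day windows, 60 × 365 / 30 = 730 windows, of which 730 − 60 = 670 are not pre-event. The background frequency, which the plan does not estimate, decides the meaning:

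| Background frequency (assumed) | Likelihood ratio | Pattern-positive windows followed by an event |
|---|---|---|
| 5% | 0.70/0.05 = 14 | 42/(42 + 33.5) = 56% |
| 20% | 3.5 | 42/(42 + 134) = 24% |
| 50% | 1.4 | 42/(42 + 335) = 11% |
| 70% | 1.0 | 42/(42 + 469) = 8% |

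The pre-event finding is identical in all four rows.

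**4. Whether reference time exists, and how clean it is.** Take an assumed distance of 60 days on either side over 12 months. For a day at least 60 days from both ends of follow-up, the surrounding span is 120 days; near the ends it is 60 to 120 days. Averaging exp(−rate × span) over the year gives 74.0% of time clear of COPD events (rate 1) and 54.9% clear of any exacerbation (rate 2). A reference that avoids only adjudicated events would therefore have (74.0 − 54.9)/74.0 = 26% of its time within 60 days of a non-qualifying exacerbation. With gamma shape 0.5 the figures are 79.1% and 67.5%, giving (79.1 − 67.5)/79.1 = 15%.

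**5. Precision of a within-subject comparison.** Poisson counts give 60 × 0.632 = 38 event subjects. By simulation, about 89.5% of them (34) have both a full 30-day pre-event window and a 30-day reference window at least 60 days from any exacerbation. The 95% half-width, in SDs of the subject-level differences, is t(0.975, n−1)/√n:

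| Assumption | n | Half-width |
|---|---|---|
| Poisson, 12 months | 34 | 0.35 |
| Poisson, 6 to 32 months | 43 | 0.31 |
| Shape 2, 12 months | 28 | 0.39 |
| Shape 0.5, 12 months | 19 | 0.48 |
| Poisson, 12 months, assumed 30% without usable windows | 34 × 0.7 ≈ 24 | 0.42 |

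The last row matters because RAMware data are overwritten if not manually transmitted within 32 days (protocol 10.11), and nothing is imputed (protocol 14.6).

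**The case against.** **Stage of research.** The study is a feasibility study with no hypothesis (protocol 14), and it claims only potential patterns and signals. Background frequency could be estimated later on the retained data. This limits the severity. It explains why there is no test, but it does not supply a reference, and the relationship is the primary objective. Protocol 14.5 also relies on a plan written before the data are analysed; choosing reference time after seeing the plots weakens that protection.

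**Partial handling.** Nothing bounds 'before', so a plot may show weeks of stable time, and an interest in changes implies some comparison within the subject. The SAP's covariate list is open-ended. These soften the gap, but none of them specifies a comparison.

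**Limits of any remedy.** These objections stand. Counting a pattern in the same pre-event windows in which it was found overstates its pre-event frequency. Data loss lowers precision. The two RAMware types differ: the LINQ HF list (7.1.5.1) includes activity and the ALLEViate-HF list (7.1.5.2) does not, while only the latter is said to calculate respiration rate. Several windows and reference groups across many signals would be too heavy for a descriptive plan, so the fix is kept to one comparison.

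**Stronger readings.** A reader might infer that the study cannot meet its objective, or that it collects no reference data. The documents do not support either. Monitoring continues throughout follow-up, event-free subjects are in the analysis set, and much of the patient-time lies away from any event. The gap is in the analysis plan. Nor can one say that device data are barred from the Cox models; they are simply not named.

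**Conclusion.** The concern holds as a gap in the analysis plan that should be closed. Followed exactly, the plan relates device data to COPD events only by inspecting plots around events, and it cannot show whether a pre-event pattern is more common than in stable time. That conclusion rests on the text and on no model.

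The sizes do rest on assumptions: Poisson or gamma-mixed counts at the plan's implied rate, 30-day windows, a 60-day distance and uniform accrual. On these, 37% of subjects have no event in 12 months (44% to 58% with overdispersion; 25% with 6 to 32 months of follow-up), and 15% to 26% of a reference that avoids only adjudicated events would lie near a non-qualifying exacerbation. Interpretation is limited; the study is not invalidated.

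**What to change.** Before the data are analysed, add to protocol 14.3.3 and SAP 7.9.3 one descriptive within-subject comparison:

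- State one pre-event window length in advance, and compare it with event-free windows of equal length in the same subjects.
- Place reference windows a pre-stated distance from any adjudicated COPD event and from any other reported pulmonary adverse event. The information is already there: the adjudication committee "will review the Pulmonary related AEs and will provide a COPD event relatedness adjudication".
- For each signal, report the mean within-subject difference with a 95% confidence interval that allows for repeated events per subject. Label it descriptive, with no hypothesis test and no multiplicity claim, and state which RAMware type supplies the signal.
- Windows from subjects without events may be shown as a secondary reference, by RAMware type.
- If a pattern found in the plots is counted in pre-event and event-free windows, either fix the pattern rule in advance or state that its pre-event frequency is optimistic because it was chosen on those windows.
- Keep all events in the main display, as protocol 14.3.2 and SAP 7.9.2 require.

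The cost is modest programming on data already collected, plus stating the window and distance in advance. Visits, sample size and data collection do not change. The report should say that precision is limited and that the half-widths worked out without data loss are a best case.
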